13.12.3. Deliverables

Delivery	Description
IA1	Interim Analysis Statistical Analysis Complete at IA (Month 4) when 50% of subjects have received their 3 rd injection.
IA2	Interim Analysis Statistical Analysis Complete at IA (Month 4) when 100% of subjects have received their 3 rd injection.

Delivery	Description
HL	Headline at Month 12
M12	Statistical Analysis Complete at Month 12
EOS	End of Study

13.12.4. Study Population Tables

Study Population Tables					
No.	Population	GSK Standard / Example Shell	Title	Programming Notes	Deliverable
Subject Disposition					
1.1.	Safety	ES1	Summary of Subject Disposition for the Subject Conclusion Record	ICH E3, FDAAA, EudraCT	HL, M12, EOS
1.2.	Safety	SD1	Summary of Treatment Status and Reasons for Discontinuation of Study Treatment	ICH E3	M12, EOS
1.3.	Safety	DISP T1	Summary of Subject Disposition at Each Study Phase	
ICH E3 Intervention/Extension phase: status and reason for withdrawal based on date and reason collected in the study treatment discontinuation form.
 
Long term Follow-up: completion/withdrawal based on data collected in the Study Conclusion form.
 
For the Intervention Phase, columns should report OLI results, LA results, & Total results; All other phases only list total results
 
Under withdrawals, add subcategory for Covid-19
	M12, EOS

Study Population Tables					
No.	Population	GSK Standard / Example Shell	Title	Programming Notes	Deliverable
1.4.	Safety	DISP_T2	Summary of Reason for Withdrawal at Each Study Phase	FDAAA, EudraCT For Intervention Phase, columns should report OLI results, LA results, & Total results; All other phases only list total results See mockup for relevant Covid-19 Subcategories	IA2, HL, M12, EOS
1.5.	Safety	ES11	Summary of Outcome of Adverse Events Which Led to Study Withdrawal/Treatment Discontinuation at Each Study Phase	EudraCT	M12, EOS
1.6.	Screened	ES6	Summary of Screening Status and Reasons for Screen Failure	Journal Requirements	M12
1.7.	Enrolled	NS1	Summary of Number of Subjects by Country and Site ID	EudraCT/Clinical Operations	IA1, HL, M12
Protocol Deviation					
1.8.	Enrolled	DV1	Summary of Important Protocol Deviations	ICH E3	M12, EOS
1.9.	Enrolled	DV1	Summary of Important COVID-19 Related Protocol Deviations	Update the label for the first row to be "ANY IMPORTANT COVID-19 RELATED PROTOCOL DEVIATIONS"	M12, EOS
1.10.	Enrolled	DV1	Summary of Important Non-COVID-19 Protocol Deviations	Update the label for the first row to be "ANY IMPORTANT NON-COVID-19 RELATED PROTOCOL DEVIATIONS"	M12, EOS
1.11.	Enrolled	DV1	Summary of COVID-19 Protocol Deviations by Site	Update the label for the first row to be "ANY COVID-19 RELATED PROTOCOL DEVIATIONS". Summary for each site and 'Total' across sites.	IA2, HL, M12, EOS

Study Population Tables					
No.	Population	GSK Standard / Example Shell	Title	Programming Notes	Deliverable
1.12.	Enrolled	DV1	Summary of All Implementation Protocol Deviations by Site	Update the label for the first row to be "ANY IMPLEMENTATION RELATED PROTOCOL DEVIATIONS" Summary for each site and 'Total' across sites.	HL, M12, EOS
Population Analysed					
1.13.	Screened	SP1	Summary of Study Populations	GSK Statistical Display Standard	M12, EOS
1.14.	Enrolled	SP2	Summary of Exclusions from the Safety Population	GSK Statistical Display Standard	M12
Demographic and Baseline Characteristics					
1.15.	Safety	DM1	Summary of Demographic Characteristics	ICH E3, FDA, EudraCT Include Baseline CD4+ Cell Count Results and CDC HIV-1 Infection Classification.	IA1, HL, M12
1.16.	Enrolled	DM11	Summary of Age Ranges	EudraCT	M12
1.17.	Safety	DM6	Summary of Race and Racial Combinations	ICH E3, FDA, FDA, EudraCT	M12
Prior and Concomitant Medications					
1.18.	Safety	MH1	Summary of Past Medical Conditions	ICH E3	M12
1.19.	Safety	MH4	Summary of Past Cardiac, Gastrointestinal, Metabolism and Nutrition, Psychiatric, Renal and Urinary, Nervous System Conditions, and Hepatobiliary Disorders	ICH E3	M12
1.20.	Safety	MH1	Summary of Current Medical Conditions	ICH E3	M12
1.21.	Safety	MH4	Summary of Current Cardiac, Gastrointestinal, Metabolism and Nutrition, Psychiatric, Renal and Urinary, Nervous System Conditions, and Hepatobiliary Disorders	ICH E3	M12

Study Population Tables					
No.	Population	GSK Standard / Example Shell	Title	Programming Notes	Deliverable
1.22.	Safety	CM9	Summary of Concomitant Medications by Ingredient Combinations	ICH E3 See GSK Statistical Display Standard Multi-ingredient medications will be labelled according to the sum of their ingredients, i.e., Generic Term.	M12, EOS
1.23.	Safety	207966/primary_15/T1.30	Summary of Prior Antiretroviral Therapy Taken during Screening	Remove the footnote. Follow definitions in Section 13.3.1 to determine the prior ART medications.	M12
1.24.	Safety	RF1	Summary of HIV Risk Factors		M12
1.25.	Safety	201585/primary_02/T1.31	Time Since First Antiretroviral Therapy Until Intervention Phase Start	Add footnote "Note: Duration is calculated as the day prior to first dose of CAB+RPV – the first recorded date of prior ART usage +1."	M12
1.26.	Safety	DM1	Summary of Categorical Baseline BMI		M12
1.27.	Safety	DM1	Summary of Baseline BMI Based on Day 1 Weight Values	Repeat the descriptive BMI statistics from Table 1.15 and the categorical statistics from Table 1.26 using a newly calculated Baseline BMI based on Day 1 weight values instead of CRF reported BMI values.	EOS

13.12.5. Efficacy Tables

Efficacy: Tables					
No.	Population	GSK Standard/ Example Shell	Title	Programming Notes	Deliverable
Snapshot					
2.1.	Safety	EFF T1	Summary of Study Outcomes (50 c/mL cutoff) at Month 12 (Intervention Phase) –Snapshot Analysis		HL, M12
2.2.	Safety	EFF T2	Summary of Study Outcomes (50 c/mL cutoff) at Month 12 (Intervention Phase) –Snapshot Analysis Considering Covid-19 Based Events	With expanded COVID-19 related/Non-related categories	HL, M12
2.3.	Safety	SNAPSHOT4	Proportion of Subjects with Plasma HIV-1 RNA \geq 50 c/mL Over Time (Intervention Phase) –Snapshot Analysis	Use Exact (Clopper-Pearson) method for 95% confidence Intervals. Expand to all visits, drop 'n' row, replace x (%) column data with x/n (%), drop '(Intervention Phase)' and use Observed Case instead of Snapshot for EOS	M12, EOS
2.4.	Safety	SNAPSHOT4	Proportion of Subjects with Plasma HIV-1 RNA < 50 c/mL Over Time (Intervention Phase) –Snapshot Analysis	Use Exact (Clopper-Pearson) method for 95% confidence Intervals. Expand to all visits, drop 'n' row, replace x (%) column data with x/n (%), drop '(Intervention Phase)' and use Observed Case instead of Snapshot for EOS	M12, EOS
2.5.	Safety	SNAPSHOT4	Proportion of Subjects with Plasma HIV-1 RNA \geq 50 c/mL Over Time by Subgroup (Intervention Phase) –Snapshot Analysis	Include the following subgroups: country, implementation arm, sex, age group, race group, and CD4 group as mentioned in Section 5.4.2.	M12

Efficacy: Tables					
No.	Population	GSK Standard/ Example Shell	Title	Programming Notes	Deliverable
2.6.	Safety	SNAPSHOT4	Proportion of Subjects with Plasma HIV-1 RNA < 50 c/mL Over Time by Subgroup (Intervention Phase) –Snapshot Analysis	Include the following subgroups: country, implementation arm, sex, age group, race group, and CD4 group as mentioned in Section 5.4.2.	M12
CVF					
2.7.	Safety	VF1	Cumulative Proportion of Subjects Meeting Confirmed Virologic Failure Criteria Over Time (Intervention Phase)		HL, M12
2.8.	Safety	VF2	Proportion of Subjects Meeting Confirmed Virologic Failure Criteria Over Time		M12, EOS
Genotype & Phenotype					
2.9.	Safety	201584/primary_17/T7.1	Summary of the Prevalence of Treatment-Emergent Major Resistance Mutations of INI, NRTI, NNRTI and PI Class at time of CVF - Plasma Sample	Known resistance mutations per Section 13.5.5. Include 95% confidence Intervals using Exact (Clopper-Pearson) method.	HL, M12, EOS
2.10.	Safety	201584/primary_17/T7.2	Summary of Viral load, Genotypic and Phenotypic data for Subjects Who Met Confirmed Virologic Failure Criteria		M12, EOS
2.11.	Safety	201584/primary_17/T7.4	Summary of Viral load, Genotypic and Phenotypic data for Subjects Who Did Not Meet Confirmed Virologic Failure Criteria	Only include subjects with available genotypic or phenotypic data.	M12, EOS
CD4					
2.12.	Safety	LB1	Summary of CD4+ Cell Count (cells/mm ³) by Visit		M12, EOS
2.13.	Safety	LB1	Summary of Change from Baseline in CD4+ Cell Count (cells/mm ³) by Visit		M12, EOS

Efficacy: Tables					
No.	Population	GSK Standard/ Example Shell	Title	Programming Notes	Deliverable
2.14.	Safety	LB1	Summary of CD4+/CD8+ Ratio Cell Count (cells/mm ³) at Baseline & Month 12		M12
HIV Associated Conditions					
2.15.	Safety	CDC2	Summary of Post-Baseline CDC Stage 3 HIV-1 Associated Conditions Including Recurrences		M12, EOS
2.16.	Safety	CDC2	Summary of Post-Baseline CDC Stage 3 HIV-1 Associated Conditions Excluding Recurrences		M12, EOS

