CAB LA + RPV LA IM Treatment Administration ⁱ			X	X	X	X	X	X	X			

213199

]		Sa						
Procedure	Screening* up to 35d	Day 1	Month 1	Month 2	Month 4	Month 6	Month 8	Month 10 b	Month 12 b	Withdrawal ^m	Safety Follow-up Visit ^w	Long Term Follow-up ⁿ
	Δ. ř	Oral Lead- in	Dose 1 (D1)	Dose 2 (D2)	Dose 3 (D3)	Dose 4 (D4)	Dose 5 (D5)	Dose 6 (D6)	Dose 7 (D7)	/alm		D B
Participant Visit Reminder Contact	х	х	х	х	х	х	х	х				
Participant Contact Detail Confirmation	x	х	х	х	х	х	х	х				
Patient Toolkit ^s		х	х	х	х			X				
Record Visit Length ^j			х	х		х	х					
Contraception Counseling ^u										х		x
HAART dispensation ^v										х		X
Patient Questionnaires ^k			X		X				х			
Selected Patient Interviews ¹		х							х			
CCI												

213199

	Screening ^a up to 35d		Intervention Period (Month)								Safe	
Procedure		Day 1	1 Month 1	Month 2	Month 4	Month 6	Month 8	Month 10	Month 12	Withdrawa1 ^m	ety Follo Visit ^w	- Long Term Follow-up ⁿ
		Oral Lead- in	Dose 1 (D1)	Dose 2 (D2)	Dose 3 (D3)	Dose 4 (D4)	Dose 5 (D5)	Dose 6 (D6)	Dose 7 (D7)		dn-wo	ip"
Preference Question									X			
Review plan to transition to commercial product or alternative ART ^v											Х	

a) A screening visit will be conducted within 35 days of Day 1. However, it is preferred for Day 1 to be conducted as soon as practical after all screening results are available.

- b) Continue this pattern for visits for the remainder of the study if needed, until CAB LA + RPV LA is locally approved and available. For example, Dose 8 will be conducted as per Dose 6, Dose 9 will be conducted as per Dose 7, Dose 10 will be conducted as per Dose 6 and so on. The exception to this pattern is that no questionnaires, study visit length collection, or patient interviews will be conducted after Dose 7 visit. Visit after Month 12 will be considered, 'extension phase.' See Section 6.8.
- c) Physical exams should be conducted as part of normal routine clinical care but data will not be collected in the electronic case report form (eCRF) unless abnormalities are observed. Medical assessments include any decisions the study staff must make for participant management.
- d) AE and SAEs will not be proactively assessed at M 2, M 6 and M 10. However, all AEs and SAEs reported by study participants **must** be recorded in eCRF at all visits and reported within required timelines as per Section 8.5.1.
- e) Measure vital signs after about 5 minutes of rest in a semi-supine position.

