4.4.2. Long-Acting Injectable Phase

Study 200056 (LATTE-2) is an ongoing, Phase 2b dose-ranging study evaluating the long-term efficacy and safety of a two-drug, two-class combination of CAB LA + RPV LA given every 4 weeks (Q4W) or every 8 weeks (Q8W), as compared to an oral 3-drug

regimen, for maintenance of virologic suppression in HIV-infected, treatment-naive adults. Following induction with16 weeks of oral CAB + 2 NRTIs, 4 weeks of CAB + 2 NRTIs + oral RPV, eligible participants were randomized (2:2:1) to receive IM CAB LA every 4 weeks (800 mg Day 1 then 400 mg Q4W) or every 8 weeks (800 mg Day 1, 600 mg Week 4, 600 mg Week 8, then 600 mg Q8W) in combination with IM RPV LA every 4 weeks (600 mg Day 1 then 600 mg Q4W) or every 8 weeks (900 mg Day 1, 900 mg Week 8, then 900 mg Q8W), respectively, or to continue on their oral triple ART regimen.

Both Q4W and Q8W regimens were continued throughout the Injection Phase as planned, and Week 96 results (Table 9) were supportive of further evaluation both the Q4W regimen in ATLAS and FLAIR as well as the Q8W regimen in the ATLAS-2M study. Subjects completing the 96-week Injection Phase remained on their randomized LA regimen (either Q4W or Q8W) during the Extension Phase (post Week 96), and those subjects randomized to the oral comparator arm were allowed transition to either LA regimen at Week 96. Forty-four subjects were transitioned from the oral comparator arm to LA treatments in the Extension Phase; 34 (77%) opted for the Q8W regimen and 10 (23%) for the Q4W regimen. Initial LA injections were administered at Week 100 following a 4-week oral lead-in where 2 NRTIs were discontinued and RPV 25 mg once daily was added to CAB 30 mg once daily.

Table 9Summary of Study Outcomes (<50 copies/mL) at Weeks 48 and 96 –
Snapshot (MSDF) Analysis (ITT-ME Population) in LATTE-2

Endpoint (Week)	Outcome	Q8W IM N=115 n (%)	Q4W IM N=115 n (%)	CAB 30 mg+ ABC/3TC N=56 n (%)	Subtotal IM N=230 n (%)
W48	Virologic Success, n (%)	106 (92)	105 (91)	50 (89)	211 (92)
VV40	Virologic Failure, n (%)	8 (7)	1 (<1)	1 (2)	9 (4)
MOC	Virologic Success, n (%)	108 (94)	100 (87)	47 (84)	208 (90)
W96	Virologic Failure, n (%)	5 (4)	0	1 (2)	5 (2)

[figure not shown]

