Total score of the Clinical Sustainability Assessment Tool (CSAT) at Month 12	Total score of the Clinical Sustainability Assessment Tool (CSAT) will be summarized using descriptive statistics including 95% confidence intervals. Data will be summarized by month of study as actual values and change from baseline.
Percentage of injections occurring within target window from the target date.	Percentage of injections occurring within target window from the target date, will be summarized at Month 12, including 95% confidence intervals
	The patient's 'target date' is determined by their first injection date
Proportion of participants with plasma HIV-1 RNA <50 c/mL over time	The proportion of participants with HIV-1 RNA <50 c/mL, based on the snapshot algorithm, will be summarized at Dose 7, with 95% confidence intervals
	The proportion of participants with HIV-1 RNA >= 50c/mL, respectively, based on the snapshot algorithm, will be summarized at Dose 7, with 95% confidence intervals.
Proportion of participants with confirmed virologic failure (CVF) over time	Summary of proportion of participants with confirmed virologic failure (CVF) over time using the FDA Snapshot algorithm in the ITT-E population
Incidence of treatment-emergent genotypic and phenotypic resistance to CAB and RPV in patient study participants with CVF	Incidence of treatment-emergent genotypic and phenotypic resistance to CAB and RPV in patient study participants with CVF will be summarized at Dose 7, with 95% confidence intervals
Incidence and severity of AEs and SAEs over time and the proportion of participants who discontinue treatment due to AEs over time	Incidence and severity of AEs and SAEs over time, will be summarized, with 95% confidence intervals. Proportion of participants who discontinue treatment due to AEs over time will be summarized.

Endpoints	Statistical Analysis Methods
Preference between CAB + RPV LA and daily oral ART medication (received prior to entering the study) quantitatively assessed via preference questionnaire at Dose 7	The proportion of participants preferences between CAB + RPV LA and daily oral ART medication (received prior to entering the study) with be summarized at Dose 7.
Reported injection site reactions over time	Reported injection site reactions over time will be summarized
Absolute values and changes in laboratory parameters over time	Absolute values and changes in laboratory parameters over time will be summarized, with 95% confidence intervals

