7.1. Secondary Efficacy Analyses

7.1.1. Endpoint / Variables

- Proportion of participants with Plasma HIV-RNA < 50 copies/mL and plasma HIV-1 RNA \geq 50 copies/mL as per Food and Drug Administration (FDA) Snapshot algorithm at Month 12 (Safety Population). See [Appendix 8](#) for Snapshot Algorithm details.
- Participants with protocol-defined confirmed virologic failure (CVF) over time (Safety population)
- Incidence of treatment-emergent genotypic and phenotypic resistance to CAB and RPV in patient study participants with CVF (Safety population)

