7.1.3. Strategy for Intercurrent (Post-Randomization) Events

Participants with last available HIV-1 RNA measurement less than 50 copies/mL while the participant is on treatment within the analysis visit window of interest are classified as HIV-1 RNA < 50 c/mL. Participants without evaluable HIV-RNA data for the visit of interest or who change treatment not permitted per protocol before the analysis window are considered non-responders.

Participants with last available HIV-1 RNA measurement greater or equal to 50 copies/mL while the participant is on treatment within the analysis visit window of interest are classified as HIV-1 RNA \geq 50 c/mL. Participants without evaluable HIV-RNA data for the visit of interest and who discontinue treatment for reasons not related to adverse event while having HIV-1 RNA \geq 50 copies/mL at time of discontinuation or who change study treatment not permitted per protocol before the analysis window are also classified as having HIV-RNA \geq 50 copies/mL.

Missing viral load values for reasons related to COVID-19 issues (e.g. participant is unable to have viral load assessed due to barriers in attending the clinic during the pandemic or COVID-19 related adverse events leading to treatment discontinuation) will

be considered as random missingness and classified the same as all other missingness for the primary efficacy Snapshot analysis. A sensitivity analysis using a modified Snapshot which includes subcategories for Covid-19 related and Non-Covid-19 related missingness will also be performed to display the impact of Covid-19 intercurrent events on the study. See [Appendix 8](#) for Modified Snapshot Algorithm details.

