13.12.6. Efficacy Figures

Efficacy: Figures					
No.	Population	GSK Standard / Example Shell	Title	Programming Notes	Deliverable
Snapshot					
2.1.	Safety	SNAPSHOT8	Percent (95% CI) of Subjects with Plasma HIV-1 RNA ≥ 50 copies/mL Over Time (Intervention Phase) –Snapshot Analysis	Use Exact (Clopper-Pearson) method for 95% confidence Intervals. Drop '(Intervention Phase)', Observed cases to be used at EOS instead of Snapshot	M12, EOS
2.2.	Safety	SNAPSHOT8	Percent (95% CI) of Subjects with Plasma HIV-1 RNA < 50 copies/mL Over Time (Intervention Phase) –Snapshot Analysis	Use Exact (Clopper-Pearson) method for 95% confidence Intervals. Drop '(Intervention Phase)', Observed cases to be used at EOS instead of Snapshot	M12, EOS

Efficacy: Figures					
2.3.	Safety	SNAPSHOT10	Individual HIV-1 RNA Plasma Profiles by Visit for Subjects with HIV-1 RNA \geq 50 copies/mL at Month 12 per Snapshot Algorithm	The 1st vertical line indicates start of study treatment at Intervention Phase. The second vertical reference line indicates last IP on-treatment study day. i.e. min (last IP injection dose+35 days, LTFU HAART start date, date of last oral CAB+RPV+1). This vertical line is only for subjects who withdraw from Intervention Phase/Extension phase.	M12
2.4.	Safety	SNAPSHOT10	Individual HIV-1 RNA Plasma Profiles by Visit for Subjects with Confirmed Virologic Failure	Same as Figure 2.3.	M12, EOS

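### At end of study the virologic tables and figures replace Snapshot with an undefined Observed Case method at every visit, giving a second and usually more favourable suppression figure for Months 1 to 12

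*SAP*

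**What the plan says.** Protocol Section 9.4.2 states that the proportions below and at or above 50 c/mL are "based on the snapshot algorithm, will be summarized at Dose 7". SAP Section 7.1.1 names the same endpoint, by the "Snapshot algorithm at Month 12 (Safety Population"). SAP Section 7 says efficacy is analysed at Month 12 and again at end of study (EOS), without announcing a different method for the second report.

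SAP Section 7.1.3 sets the missing-data rule: participants with no evaluable HIV-1 RNA at the visit of interest, or with a non-permitted treatment change "before the analysis window are considered non-responders". It also counts as viraemic those who stop for reasons other than an adverse event while at 50 c/mL or more. Appendix 8 carries this into the algorithm: non-safety withdrawals whose last on-treatment value was 50 c/mL or more go in the viraemic row.

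The EOS notes depart from this. For Tables 2.3 and 2.4 (SAP 13.12.5) the programmer is to drop the Intervention Phase label, expand to all visits and "use Observed Case instead of Snapshot for EOS". For Figures 2.1 and 2.2 (SAP 13.12.6) the note reads "Observed cases to be used at EOS instead of Snapshot". SAP 13.12 says that displays not restricted by title span both Intervention and Extension phases, so visits through Month 12 are included. No section defines Observed Case.

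**The concern.** The same visits would be reported twice by two methods. At the Month 12 report, a participant with no value in the window stays in the denominator. At EOS that participant disappears, including one who stopped with viraemia before the window. The EOS percentages at Intervention visits are therefore conditional on still being sampled, and a reader of the EOS report alone would see them without the Snapshot counterpart: Tables 2.1, 2.2, 2.5 and 2.6, Figure 2.3 and Listing 11 are not EOS deliverables.

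The missing definition matters in its own right. Snapshot uses the last on-treatment value in the window (SAP 13.5.3). Ordinary visit summaries use the value closest to the target day (SAP 13.5.1). Protocol Section 7.1.8.1 asks for a retest within the same window when the Month 12 value is 50 c/mL or more. One participant could thus be suppressed by Snapshot on the retest and viraemic under Observed Case on the scheduled sample. Whether off-treatment values count is also unstated.

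**Working it through.** **Inputs.** SAP Section 2.4.1 gives 450 evaluable, 5% non-evaluable and 10% screen failures. These reproduce the plan's own figures: 450/0.95 = 473.7, so 474 enrolled; 474/0.90 = 526.7, so 527 screened. The implied number non-evaluable is 474 − 450 = 24. The documents give no figure for the difference between the two methods.

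**Notation at one visit.** N = all participants; S = below 50 with an on-treatment value in window; fw = at or above 50 with a value in window; fd = counted at or above 50 by Snapshot without a value in window; M = no virologic data. So N = S + fw + fd + M. Observed Case is taken to use the same on-treatment value as Snapshot.

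- Snapshot: suppressed = S/N; viraemic = (fw + fd)/N.
- Observed Case: suppressed = S/(S + fw); viraemic = fw/(S + fw).

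**Suppression.** S is the same in both methods and S + fw ≤ N, so Observed Case is never lower than Snapshot.

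**Viraemia.** Observed Case is lower only when fw/(N − M − fd) < (fw + fd)/N, which rearranges to fd/(fw + fd) > (M + fd)/N. Otherwise it is equal or higher.

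**Planned numbers.** N = 474 with 24 lacking window data (M + fd = 24). Ten viraemic participants are assumed, and the split between fw and fd is varied:

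| fw, fd | Snapshot <50 | Observed Case <50 | Snapshot ≥50 | Observed Case ≥50 |
|---|---|---|---|---|
| 10, 0 | 440/474 = 92.8% | 440/450 = 97.8% | 10/474 = 2.1% | 10/450 = 2.2% |
| 9, 1 | 441/474 = 93.0% | 441/450 = 98.0% | 2.1% | 9/450 = 2.0% |
| 5, 5 | 445/474 = 93.9% | 445/450 = 98.9% | 2.1% | 5/450 = 1.1% |
| 0, 10 | 450/474 = 94.9% | 450/450 = 100% | 2.1% | 0/450 = 0% |

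Suppression gains about 5 points in every row. The threshold for viraemia to fall is 24/474 = 5.1% of failures lacking window data; 1 in 10 already exceeds it.

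**Illustration from another trial.** Protocol Table 9 gives, for the every-8-weeks arm of LATTE-2 at Week 48, 106 successes and 8 failures among 115, leaving 115 − 106 − 8 = 1 in neither row. Snapshot suppression is 106/115 = 92.2%. Observed Case is 106/114 = 93.0% if all 8 failures had window data, and 106/106 = 100% if none did. Viraemia goes from 8/115 = 6.96% to 8/114 = 7.02% in the first case and to 0% in the second.

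**Extension visits.** Suppose half of 450 move to commercial supply and 98% of the remaining 225 are suppressed (both assumptions). Observed Case gives 220/225 = 97.8%; a fixed denominator gives 220/474 = 46.4%. A fixed-denominator Snapshot would mislead there.

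**The case against.** The strongest reply is that nothing is replaced. Protocol Section 9.4.2 requires Snapshot at Dose 7 only, and that result is delivered at headline and Month 12 in Tables 2.1 and 2.2, with Tables 2.3 to 2.6 at Month 12. The objective-level wording is over time, with no algorithm named. The EOS note also tells the programmer to "replace x (%) column data with x/n", so the shrinking denominator is printed in the tables. After Month 12, planned exits to commercial supply (Protocol 4.5.1.2) make some form of observed-case display sensible. All of this stands. It leaves unexplained why Intervention visits, where commercial exit is not the reason for missing data, are re-reported under a rule opposite to Section 7.1.3.

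Four stronger readings are tempting but not supported.

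- **The trial's endpoint has been swapped.** It has not, for the reasons just given.
- **Viraemia is always understated.** Participants at 50 c/mL or more with a value in window stay in both numerator and denominator, and the percentage can rise slightly. Protocol Section 7.1.8.3 lets confirmed failures stay on study drug until resistance results arrive, so they need not vanish at once.
- **Failures become invisible at EOS unless Table 2.7 is redelivered.** Tables 2.8 to 2.10, Figure 2.4 and Listing 12 are all EOS deliverables and show confirmed failures. Table 2.7 is limited to the Intervention Phase and would add almost nothing.
- **Expanding to all visits brings in visits with no scheduled HIV-1 RNA.** Footnote b of the Schedule of Activities ("Dose 8 will be conducted as per Dose 6, Dose 9 will be conducted as per Dose 7") does create such Extension visits, but SAP 13.2.1 and 13.4.2 already limit visit summaries to planned assessments.

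**Conclusion.** The concern holds in a limited form. At EOS, Tables 2.3 and 2.4 and Figures 2.1 and 2.2 apply an undefined method to Intervention visits that conflicts with SAP Section 7.1.3 and Appendix 8. The result is a second Month 12 suppression figure, equal to or higher than the Snapshot one: about 5 points higher if the planned 24 of 474 non-evaluable participants are those without window data. The viraemic figure can move either way; it falls once the share of failures without window data exceeds the share of all participants without it.

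The size rests on three assumptions: that non-evaluable means no HIV-1 RNA in the Month 12 window, that 10 participants are viraemic, and that Observed Case would use the same on-treatment value as Snapshot. If it used the value closest to target, or off-treatment values, the direction could differ for individual participants. The LATTE-2 counts are illustrative only. The Month 12 conclusion of the trial is not affected.

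**What to change.** Amend the notes to Tables 2.3 and 2.4 and Figures 2.1 and 2.2 as follows:

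1. At EOS, keep Snapshot for Intervention visits through Month 12.
2. Restrict Observed Case to Extension visits and label it supplementary.
3. Define it there: which value in the window is used, and that only on-treatment values count.
4. State beside it the number who stopped for lack of efficacy or with last HIV-1 RNA of 50 c/mL or more.
5. Correct the Snapshot Analysis titles for the Extension part.

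No new data are needed. The cost is modest reprogramming, a display that uses two methods on either side of Month 12 and must be labelled as such, and slightly less favourable suppression figures at EOS.
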